## 17.0 Multi-Site Study

### 17.1 Other sites

Not applicable

### 17.2 Communication Plans

Not applicable

### 17.3 Data Submission and Security Plan

Not applicable

### 17.4 Subject Enrollment

Not applicable

### 17.5 Reporting of Adverse Events and New Information

Not applicable

### 17.6 Audit and Monitoring Plans

Not applicable

## 18.0 Adverse Event Reporting

### 18.1 Adverse Event Definitions

For drug studies, incorporate the following definitions into the below responses, as written:	
Adverse event	Any untoward medical occurrence associated with the use of the drug in humans, whether or not considered drug related
Adverse reaction	Any adverse event caused by a drug
Suspected adverse reaction	Any adverse event for which there is a reasonable possibility that the drug caused the adverse event. Suspected adverse reaction implies a lesser degree of certainty about causality than “adverse reaction”. 

• Reasonable possibility. For the purpose of IND safety reporting, “reasonable possibility” means there is evidence to suggest a causal relationship between the drug and the adverse event.

Serious adverse event or Serious suspected adverse reaction	Serious adverse event or Serious suspected adverse reaction: An adverse event or suspected adverse reaction that in the view of either the investigator or sponsor, it results in any of the following outcomes: Death, a life-threatening adverse event, inpatient hospitalization or prolongation of existing hospitalization, a persistent or significant incapacity or substantial disruption of the ability to conduct normal life functions, or a congenital anomaly/birth defect. Important medical events that may not result in death, be life-threatening, or require hospitalization may be considered serious when, based upon appropriate medical judgment, they may jeopardize the patient or subject and may require medical or surgical intervention to prevent one of the outcomes listed in this definition.
Life-threatening adverse event or life-threatening suspected adverse reaction	An adverse event or suspected adverse reaction is considered “life-threatening” if, in the view of either the Investigator (i.e., the study site principal investigator) or Sponsor, its occurrence places the patient or research subject at immediate risk of death. It does not include an adverse event or suspected adverse reaction that had it occurred in a more severe form, might have caused death.
Unexpected adverse event or Unexpected	An adverse event or suspected adverse reaction is considered “unexpected” if it is not listed in the investigator brochure, general investigational plan, clinical

suspected adverse reaction.	protocol, or elsewhere in the current IND application; or is not listed at the specificity or severity that has been previously observed and/or specified.
------------------------------------	------------------------------------------------------------------------------------------------------------------------------------------------------------

For device studies, incorporate the following definitions into the below responses, as written:	
Unanticipated adverse device effect	Any serious adverse effect on health or safety or any life-threatening problem or death caused by, or associated with, a device, if that effect, problem, or death was not previously identified in nature, severity, or degree of incidence in the investigational plan or IDE application (including a supplementary plan or application), or any other unanticipated serious problem associated with a device that relates to the rights, safety, or welfare of subjects.

## 18.2 Recording of Adverse Events

Subjects will be encouraged to spontaneously report any AE. Study personnel will ask open-ended questions to obtain information about AEs at every visit. Date and time of onset and resolution (if applicable) of the AE will be documented. All AEs occurring after the initiation of the study treatment (treatment emergent adverse events) will be reported, including events present at baseline that worsened during the study.

Safety will be assessed by the investigator in the form of evaluation of adverse events and clinical laboratory results and derived as data sets and frequency methods, recorded for this study. AEs by severity and causality as described below:

- Laboratory evaluations including liver function tests. Laboratory values within 1.5x the institutional upper limit of normal are considered acceptable and not as AEs

To monitor any risk of increased surgical complications associated with posaconazole, the treating surgeons will make a Note-to-File recording any unexpected events that occurred during surgery.

Patients unable to tolerate posaconazole due to AE grade 3-4 (hepatic, gastroenterological, and/or renal toxicity) will have a dose reduction. Posaconazole will be reduced to 33% of schedule dose (200 mg per dose, see table below). If the AE does not resolve within 24 hours, it will be discontinued. However, tumor tissue will still be collected and analyzed.

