### **3.3 Early Withdrawal of Subjects**

#### **3.3.1 Criteria for removal from study**

A participant should be withdrawn from the trial treatment if, in the opinion of the PI, it is medically necessary, or if it is the wish of the participant. If a participant does not return for a scheduled visit, every effort will be made to contact the participant. In any circumstance, every effort will be made to document participant outcome, if possible.

Participants should be removed from therapy if any of the following occurs:

- Adverse event: The occurrence of unacceptable toxicity indicating the need for cessation of treatment
- The physician feels it is in the best interest of the patient to stop treatment
- The participant desired to withdraw from further participation in the study in the absence of an investigator-determined medical need to withdraw. If a reason for withdrawal is given, it should be recorded in the case report form
- Protocol violation: The participant 's findings or conduct failed to meet the protocol entry criteria or failed to adhere to the protocol requirements (e.g. study drug compliance, returning for the specified number of visits)
- Participant is lost to follow-up. If a participant does not return for scheduled visits, every effort should be made to re-establish contact. In any circumstance, every effort should be made to document participant outcome, if possible

- Participant becomes pregnant
- Termination of the study

The reason and date of discontinuation are to be documented in the participant 's medical record and in the case report form. All participants who receive one or more doses of study treatment should be included in any safety analysis. The PI may discontinue the trial at any time. Reasons for early trial discontinuation may include, but are not limited to, unacceptable toxicity of study treatment, a request to discontinue the trial from a regulatory authority, or poor enrollment.

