##### Pharmacokinetics of delayed-release Posaconazole tablets:

When given orally in healthy volunteers, posaconazole delayed-release tablets are absorbed with a median Tmax of 4 to 5 hours. The elimination half-life of posaconazole has been estimated to vary between 15-35 hours [56]. Steady-state plasma concentrations are attained by Day 6 at the 300 mg dose (QD after BID loading dose at Day 1).

The absolute bioavailability of the oral delayed-release tablet is approximately 54% under fasted conditions. The Cmax and AUC of posaconazole following administration of posaconazole delayed-release tablets is increased 16% and 51%, respectively, when given with a high fat meal compared to a fasted state. In order to enhance the oral absorption of posaconazole and optimize plasma concentrations, posaconazole delayed-release tablets should be administered with food.

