#### **7.4.6 Receiving, Storage, Dispensing and Return**

##### **7.4.6.1 Receipt of Test Article**

A study specific supply of FDA-approved posaconazole 100mg tablets will be purchased from a pharmacy wholesaler for use in this study. The manufacturer, lot number, and expiration date of the purchased posaconazole tablets will be maintained in the drug accountability records kept by the IDS pharmacy.

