### Posaconazole Dose Modification for Adverse Reactions

Dose Level	Posaconazole dose
Starting Dose	300 mg once daily
Dose Reduction (33%)	200 mg once daily

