### **18.7 Stopping Rules**

Trial accrual will be prematurely stopped if two or more unacceptable toxicities occur. Unacceptable toxicity is defined as mortality or grade 4 toxicity directly attributed to drug.

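### Section 18.2 misstates the reduced dose as a percentage and, for drug-attributed grade 4 hepatic, GI or renal toxicity, orders a lower dose where 3.3.1 read with 18.7 points to stopping

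*Combined protocol and SAP*

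**What the plan says.** Section 18.2 (Recording of Adverse Events) contains the only dose-modification rule in the combined protocol and SAP. The trigger is: "Patients unable to tolerate posaconazole due to AE grade 3-4 (hepatic, gastroenterological, and/or renal toxicity) will have a dose reduction". The size of the change is: "Posaconazole will be reduced to 33% of schedule dose (200 mg per dose, see table below". The next step is: "If the AE does not resolve within 24 hours, it will be discontinued". Section 18.2 then adds that tumour tissue is collected and analysed in any case.

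The table that follows starts from 300 mg once daily and labels 200 mg once daily as a 33% reduction. Sections 7.2.1 and 7.4.2 give the same schedule: 300 mg twice on day 1, then 300 mg once daily. Section 7.4.6.1 says the supply is 100 mg tablets.

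Two other sections bear on the same patient. Section 3.3.1 lists events on which a participant should come off therapy. Its adverse-event item reads: "The occurrence of unacceptable toxicity indicating the need for cessation of treatment". Section 18.7 halts accrual after two or more unacceptable toxicities and defines the term: "Unacceptable toxicity is defined as mortality or grade 4 toxicity directly attributed to drug". No other definition appears. Section 3.3.1 also says that a participant should be withdrawn where the PI considers it medically necessary, and taken off therapy where the physician thinks that is best for the patient.

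**The concern.** There are two separate faults in one live toxicity instruction.

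The first is arithmetic. The percentage and the milligram figure in the same sentence do not agree. With 100 mg tablets, the dose that the percentage implies (about one tablet) and the stated dose (two tablets) can both be dispensed, so the supply itself would not expose the error.

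The second is a conflict between rules. A patient with a grade 4 hepatic, gastrointestinal or renal event attributed directly to posaconazole meets the trigger in 18.2, which gives a lower dose and a wait of up to 24 h. The same patient meets the 18.7 definition of unacceptable toxicity, and 3.3.1 names unacceptable toxicity as a reason to come off therapy. Two such events would halt accrual for the whole trial, yet 18.2 directs further dosing of the person who has one. Section 11.1 promises participants no direct benefit, so the extra dose has no therapeutic purpose for that patient.

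**Working it through.** **Dose arithmetic**

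Inputs: scheduled dose 300 mg once daily (7.2.1, 7.4.2 and the dose-modification table); reduced dose 200 mg (18.2 and the table).

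- Reproducing the plan's 200 mg: a cut by one third gives 300 × (1 − 1/3) = 200 mg, or 200/300 = 66.7% of schedule. This agrees with the table.
- As worded in 18.2: 0.33 × 300 = 99 mg, about one tablet and half of what the table gives.
- Could the base be the day-1 total of 600 mg? 600/3 = 200 mg, so the number would fit. But 18.2 states the figure per dose, and the table starts from 300 mg once daily, so this reading fails.

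**Which events conflict**

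| Event (hepatic, GI or renal, not tolerated) | 18.2 | 3.3.1 read with 18.7 | Conflict? |
|---|---|---|---|
| Grade 3 | Reduce; stop if unresolved at 24 h | Not in the 18.7 definition | No |
| Grade 4, not attributed directly to drug | Same | Not in the 18.7 definition | No |
| Grade 4, attributed directly to drug | Same, no exception | In the definition; points to removal | Yes |

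**Exposure over the 24 h wait**

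Inputs: half-life t of 15-35 h (7.4.1) and the stated mean of 26-31 h (7.2.1, 7.4.2). Dosing is once daily, so about one further 200 mg dose falls in the 24 h.

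Assumptions: one-compartment decline, exposure proportional to dose, and a 300 mg steady state before the change. Time runs from the first altered or omitted dose.

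Let r = 2^(−24/t), and set the 300 mg steady-state trough to 1. At steady state the carry-over is r, so each 300 mg dose contributes 1 − r to the next trough.

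- Stopped: trough at 24 h = r.
- Reduced to 200 mg: trough at 24 h = r + (2/3)(1 − r) = 2/3 + r/3.

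| Half-life | Stopped | 200 mg |
|---|---|---|
| 15 h | 0.330 | 0.777 |
| 26 h | 0.527 | 0.842 |
| 31 h | 0.585 | 0.862 |
| 35 h | 0.622 | 0.874 |

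Across 15-35 h, the trough is 78-87% of the 300 mg trough on the reduced dose, against 33-62% if stopped. At the stated mean half-life the figures are 84-86% against 53-58%. Over the 24 h that 18.2 allows, the reduced dose therefore lowers exposure far less than stopping does.

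**The case against.** The case on the other side has real weight.

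- **The percentage is a slip of one word.** The correct milligram figure stands in the same sentence and in the table. A reader might infer that patients would be given 100 mg. The documents do not support that, because 200 mg is stated twice.
- **The 18.7 definition was written for another purpose.** It sits in an accrual rule and includes death, which cannot serve as a reason to take a living patient off drug.
- **Section 3.3.1 leaves room for judgement.** It qualifies the toxicity as one that indicates a need to stop. On that reading, 18.2 could be the specific rule that says when stopping is needed, and the sections would fit together.
- **The clinician can act.** A reader might infer that the protocol forces an investigator to keep dosing a patient in danger. It does not, because 3.3.1 says the patient should be withdrawn when the PI finds it medically necessary or the physician thinks it best.

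These points soften the conflict but do not remove it. Section 18.2 is mandatory in form, spans grades 3 and 4, and makes no exception for drug-attributed grade 4 events. Section 18.7 holds the only definition of a term that 3.3.1 uses. No sentence ranks the two, so the reconciling reading has to be supplied by the reader.

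A reader might also infer that 200 mg patients damage the primary PK analysis or have unclear status. The documents do not support this. Section 8.2 counts patients who take the drug as the protocol specifies, and a reduction under 18.2 is a protocol specification. If exposure is proportional to dose, a lower dose can only lower measured levels, so it could not create a false success on the 5 µM criterion.

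**Conclusion.** Both parts hold, and both are minor. The percentage in 18.2 is wrong: as worded it gives 99 mg, where the intended dose is 200 mg, or 67% of schedule. The intended dose can be recovered.

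The conflict between rules is confined to grade 4 hepatic, gastrointestinal or renal toxicity attributed directly to drug. Its size is about one further 200 mg dose, with a 24 h trough of 78-87% of the 300 mg trough against 33-62% if stopped, under the assumptions given above. The documents give no rate for such events and the treated arm is five evaluable patients, so how often this would arise cannot be stated.

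The dose arithmetic rests on nothing beyond the stated doses. The conflict rests on carrying the 18.7 definition into 3.3.1, which is reasonable because it is the only one offered, though the text does not expressly require it.

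**What to change.** In section 18.2:

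1. State that posaconazole is *reduced by 33%, to 200 mg once daily*.
2. Limit dose reduction to grade 3-4 events that do not meet the 18.7 definition.
3. Discontinue posaconazole at once for grade 4 toxicity attributed directly to drug, with a cross-reference to 3.3.1 and 18.7.
4. Keep the existing sentence on collecting and analysing tumour tissue.

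Say also how direct attribution is judged. Section 18.3 treats events of questionable relationship as drug-associated for reporting. Without a ruling, a grade 4 event of uncertain cause would still receive 200 mg.

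If the amendment deals with replacing a stopped patient, it should say which section governs. Section 3.3.2 allows replacement only where the reason is something other than an adverse event or unacceptable toxicity, while 8.2 replaces every non-evaluable patient.

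The cost is a few sentences. The downside is that a patient stopped at once loses steady-state PK data, which matters in an arm of five.

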### Posaconazole Dose Modification for Adverse Reactions

Dose Level	Posaconazole dose
Starting Dose	300 mg once daily
Dose Reduction (33%)	200 mg once daily

### Pregnancy statement

During the course of the trial, all patients of childbearing potential should be instructed to contact the treating physician immediately if they suspect they might have conceived a child. In addition, a missed or late menstrual period should be reported to the treating physician. If a female patient or the treating physician suspects that the female patient may be pregnant prior to administration of study drugs, the study drugs must be withheld until the results of a pregnancy test are available. If pregnancy is confirmed the patient must not receive study medications and must be withdrawn from the study. Throughout the entire pregnancy, additional contact should be made with the patient, and in some cases with the healthcare provider, to identify spontaneous abortions and elective terminations, as well as any medical reasons for elective termination. In addition, the study investigator should include perinatal and neonatal outcome. Infants should be followed for a minimum of 30 days.

If a male patient is suspected of having fathered a child while on study drugs, the pregnant female partner must be notified and counseled regarding the risk to the fetus. In addition, the treating physician must follow the course of the pregnancy, including prenatal and neonatal outcome. Infants should be followed for a minimum of 30 days.

Upon live-birth delivery, the minimum information that should be collected includes date of birth, length of pregnancy, sex of infant, major and minor anomalies identified at birth. Outcomes can be obtained via mailed questionnaires, maternal interviews, medical record abstraction, or a combination of these methods.

### **18.3 Causality and Severity Assessments**

The investigator will promptly review documented adverse events and abnormal test findings to determine 1) if the abnormal test finding should be classified as an adverse event; 2) if there is a reasonable possibility that the adverse event was caused by the study drug(s) or device(s); and 3) if the adverse event meets the criteria for a serious adverse event.

If the investigator's final determination of causality is "unknown and of questionable relationship to the study drug(s) or device(s)", the adverse event will be classified as associated with the use of the study drug(s) or device(s) for reporting purposes. If the investigator's final determination of causality is "unknown but not related to the study drug(s) or device(s)", this determination and the rationale for the determination will be documented in the respective subject's case history.

### **18.4 Reporting of Adverse Reactions and Unanticipated Problems to the FDA**

Not applicable

#### **18.4.1 Written IND/IDE Safety Reports**

Not applicable

#### **18.4.2 Telephoned IND Safety Reports – Fatal or Life-threatening Suspected Adverse Reactions**

Not applicable

### **18.5 Reporting Adverse Reactions and Unanticipated Problems to the Responsible IRB**

In accordance with applicable policies of The Pennsylvania State University Institutional Review Board (IRB), the investigator will report, to the IRB, any observed or reported harm (adverse event) experienced by a subject or other individual, which in the opinion of the investigator is determined to be (1) unexpected; and (2) probably related to the research procedures. Harms (adverse events) will be submitted to the IRB in accordance with the IRB policies and procedures.

### **18.6 Unblinding Procedures**

Not applicable

### **18.7 Stopping Rules**

Trial accrual will be prematurely stopped if two or more unacceptable toxicities occur. Unacceptable toxicity is defined as mortality or grade 4 toxicity directly attributed to drug.

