## 2.3

### Study Rationale

Both ketoconazole and posaconazole are FDA-approved anti-fungal agents with a well-established side effect and safety profile. Ketoconazole and posaconazole have shown efficacy in reducing tumor cell proliferation in our *in vitro* studies. Furthermore, both have also shown efficacy, mediated at least in part through inhibition of HK2 activity, in our animal models with dosing concentration and schedules that are documented as safe in humans.[58] As a drug, posaconazole has a more predictable half-life than ketoconazole and has less off-target effects. Therefore, the proposed trial will focus on the role of posaconazole exclusively. As a first step, demonstration of adequate penetrance of study drug in brain and tumor tissue (pharmacokinetics) and biological effect (inhibition of glycolysis and subsequent tumor cell death) is necessary prior to large scale clinical studies. A total of 5 control participants will be included in this study as we specifically want to assess for pharmacodynamic differences too. The

addition of a control group to this study rather to both the studies (ketoconazole study is a separate protocol) is because we feel posaconazole may be a more promising drug for moving forward.

Plasma drug concentration measurements are an unreliable method to assess delivery of drugs across the blood-brain barrier. In contrast, intracerebral MDC monitoring allows for approximate measurements within extracellular fluid (ECF) sampling of the brain. MDC placement within the brain is not a novel technique and has been utilized routinely in the ICU setting to measure brain metabolism by sampling of ECF of traumatic brain injury patients [59-61].

MDC are now FDA-approved and are being placed routinely with intracranial pressure monitors. This method allows for continuous measurement of ECF within a tumor or normal tissue. The dialysis probe has a semipermeable membrane which is less than 1 mm in diameter into which two sections of microcatheter are fused. Previous studies have demonstrated the feasibility of keeping the catheters in place of critically injured patients for up to 2 weeks [62-64].

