#### **9.4 Frequency of data collection**

Data collection will occur as follows:

- Laboratory data:
  - Once – Resected tumor, blood samples, and dialysate samples will be analyzed in batch
- Clinical safety data:
  - Monitored at every study visit (please refer to schedule of events)

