#### **9.8 Suspension of research**

This is pilot study, but after periodic evaluation of study result and safety profile, the PI can terminate the research anytime based on outcomes of periodic safety monitoring and benefit/risk outcomes and will inform the IRB if such a decision is being made.

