### **10.0 Risks**

#### **Risk of drug**

While this drug has never been tested specifically in the HGG population, it is an FDA-approved drug. The potential side effects are:

Common side effects (occurring in at least 1 in 100 patients) are:

- Headache
- Dizziness
- numbness or tingling;
- sleepiness
- feeling or being sick
- loss of appetite
- stomach pain
- diarrhea
- upset stomach
- nausea
- vomiting
- flatulence (excessive gas in the digestive tract)
- dry mouth
- abnormal liver function tests
- rash
- weakness
- tiredness
- a decrease in white blood cells (that can increase the risk of infections)
- fever

- abnormal amounts of salts in the blood

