## **11.0 Potential Benefits to Subjects and Others**

### **11.1 Potential Benefits to Subjects**

There will be no direct benefit to study participants.

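### The stopping rule in section 18.7 counts a death as one of two required toxicities, so the protocol states no stop or hold after a single posaconazole-related death

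*Combined protocol and SAP*

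**What the plan says.** Section 18.7 (Stopping Rules) has two sentences: "Trial accrual will be prematurely stopped if two or more unacceptable toxicities occur" and "Unacceptable toxicity is defined as mortality or grade 4 toxicity directly attributed to drug". It sets no separate or lower threshold for death.

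Other sections bear on what happens after a serious event:

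- Section 3.3.1: "The PI may discontinue the trial at any time".
- Section 9.8: "the PI can terminate the research anytime based on outcomes of periodic safety monitoring".
- Section 9.4 has clinical safety data monitored at each study visit, and section 18.3 has the investigator review adverse events promptly for causality and seriousness.
- Section 18.5 sends to the IRB those harms that the investigator considers unexpected and probably related to the research.
- Section 19.1.2 makes the CI DSMC the safety monitor and has it notified of serious adverse events.

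On benefit and risk, section 11.1 states "There will be no direct benefit to study participants". Section 10.0 says "While this drug has never been tested specifically in the HGG population, it is an FDA-approved drug", and section 2.3 describes ketoconazole and posaconazole as "FDA-approved anti-fungal agents with a well-established side effect and safety profile".

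**The concern.** In a short-exposure study with no therapeutic aim, one death related to the drug would ordinarily prompt a pause before anyone else starts it. Here the written rule treats that death as half of what is needed to stop. With five evaluable patients planned for the drug arm, two events amount to 2/5 = 40% of that target.

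What is at stake is the next patient. After one such death, a further patient could begin posaconazole before the committee has looked at the case, unless someone chooses to intervene. The purpose of a written stopping rule is that the response to the gravest event should not depend on that choice.

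**Working it through.** **Is there a figure to reproduce?** No. The threshold of two comes with no toxicity rate, error level or operating characteristic. Section 8.2 says the sample size rests on affordability and not on statistical grounds. The point therefore rests on the text.

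**Reading the rule.** One death adds one to the count. Since 1 < 2, the rule does not fire. The definition leaves open whether attribution to the drug qualifies mortality or only grade 4 toxicity, but on either reading one death is one event.

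**Does any other section require a hold after one event?**

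| Section | What it provides | Hold stated? |
|---|---|---|
| 3.3.1, 9.8 | Investigator may end the trial | No, discretionary |
| 9.4, 18.3 | Safety monitoring at visits; prompt causality review | No |
| 18.2 | Dose cut, then discontinuation, for a patient with certain grade 3-4 toxicities | No, acts on that patient only |
| 18.5 | IRB report of harms judged unexpected and probably related | No |
| 19.1.1 | Monitoring of adverse event reporting | No |
| 19.1.2 | CI DSMC oversight and notification | No |

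**How many patients are exposed?** Section 7.1 plans five evaluable patients in the drug group. That is a target and not a cap. Section 7.2.3 makes patients without high-grade glioma at surgery screen failures after they have been dosed, and section 8.2 (Study Population) replaces non-evaluable patients. I use n = 5, and n = 8 as an assumed higher figure.

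**Illustrative probabilities.** The documents give no rates, so these are assumptions: d = drug-related death rate per patient, 0.1% to 1%; p = total rate of counted unacceptable toxicity per patient including death, 1% to 10%; patients independent; no patient contributes two events.

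Chance of at least one such death = 1 − (1 − d)^n:

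- n = 5: 1 − 0.999^5 = 0.0050; 1 − 0.99^5 = 0.0490
- n = 8: 1 − 0.999^8 = 0.0080; 1 − 0.99^8 = 0.0773

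Chance of one death and no other counted toxicity, so that the rule never fires = n × d × (1 − p)^(n−1):

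| n | d | p = 1% | p = 5% | p = 10% |
|---|---|---|---|---|
| 5 | 0.1% | 0.0048 | 0.0041 | 0.0033 |
| 5 | 1% | 0.0480 | 0.0407 | 0.0328 |
| 8 | 0.1% | 0.0075 | 0.0056 | 0.0038 |
| 8 | 1% | 0.0746 | 0.0559 | 0.0383 |

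For example, 5 × 0.01 × 0.99^4 = 0.0480.

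If patients start one at a time and the death is equally likely at any position in the sequence, the mean number still to start is (n − 1)/2: 2.0 for n = 5 and 3.5 for n = 8. This supposes that nobody acts on the death.

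**The case against.** The strongest reply is that the gap may be closed in practice. The drug is licensed and its safety profile known, and preoperative exposure is only 168-240 hours. Section 7.2.2 adds an ECG and metabolic panel about three days into dosing. A responsible investigator would almost certainly pause after a drug death. The CI DSMC and the IRB work under procedures that are not in the documents, and either may require a hold. All of this stands, and it limits the point to what the protocol itself states.

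The magnitude is also open to attack, fairly. Nothing in the documents supports a death rate as high as 1%, and section 10.0 gives no rate for liver failure, which it lists as infrequent. The percentages show scale under assumption and are not estimates.

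A further reply is that the rule counts toxicities and not patients, so a grade 4 toxicity that progresses to death might count twice and trigger the stop. The text does not say so, and a safeguard should not rest on that ambiguity.

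Three stronger readings are tempting and should be resisted:

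- A reader might infer that no hold would apply at all. The documents cannot show that, because the committee and IRB procedures are outside them.
- A reader might infer from section 9.6, which plans one cumulative review at study end, that a death would go unexamined until then. Sections 9.4, 18.3 and 19.1.2 provide for review and notification as events occur.
- A reader might take the upper percentages as the risk in this trial. They come from assumed rates.

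**Conclusion.** The point holds in a limited form. As the protocol is written, one posaconazole-related death triggers no stated stop or hold; what follows is discretion, monitoring and notification. That conclusion needs no assumed rate.

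The gap is of low probability. Under the assumed death rates, at least one such death would occur in 0.5% to 4.9% of trials with five dosed, or 0.8% to 7.7% with eight. The primary endpoint, the 24-hour AUC of drug in dialysate, is unaffected. This is an inexpensive safety improvement to a stated threshold, and it does not call the trial's main result into question.

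**What to change.** Add to section 18.7: after any one death judged at least possibly related to posaconazole, new posaconazole starts in the drug arm are held until the CI DSMC has reviewed the death. This should include deaths in the section 18.3 category where causality is unknown and the relationship questionable, which that section already treats as drug-associated for reporting. For patients already on drug, the investigator decides case by case with the CI DSMC. The stop at two or more unacceptable toxicities stays unchanged.

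The wider trigger matters because deaths here may follow craniotomy and catheter placement. If the hold applied only to deaths already attributed firmly to the drug, it would depend on a difficult judgement by the investigator.

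An automatic halt to dosing is not proposed. Doses are timed backwards from surgery (section 7.2.1), and missing more than three takes a patient off study (section 8.3, Off Study Criteria). A halt could therefore make patients non-evaluable and lead to replacement exposures.

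The cost is a few sentences, since the CI DSMC already receives serious event notices. The downside is an enrolment delay in the drug arm, of unknown length because the documents do not give committee review times, including when the death proves unrelated. Surgery is planned 7-10 days after Visit 1, so a patient who cannot wait may be lost to that arm. The amendment should say whether such a patient follows the existing referral order in section 7.2, first to the ketoconazole study and then to the control arm.
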